2.2 Secondary Objectives

All Phases:

- To characterize the safety profile of MM-398 in the presence of FMX
- To assess tumor response to treatment
- To characterize the pharmacokinetics (PK) of MM-398

Pilot Phase (Completed):

- To estimate the correlations between FMX-MRI, TAM levels, and tumor levels of irinotecan and SN-38 with administration of MM-398
- To determine the value of FMX-MRI in directing tissue biopsy

Expansion Phase:

- To characterize the efficacy of MM-398 in patients with locally advanced or metastatic breast cancer using key efficacy indicators such as objective response rate and clinical benefit rate
- To assess the association between deposition, as visualized by ferumoxytol imaging, and measures of efficacy
- To further characterize the safety profile of MM-398, in the presence of FMX, in patients with metastatic breast cancer
- To assess the analytical performance of FMX-MRI measurements and optimize FMX-MRI parameterization

2.3 Exploratory Objectives

Pilot Phase (Completed):

- To estimate the correlations between potential pharmacodynamic (PD) markers (FMX-MRI, TAM, tumor irinotecan, tumor SN-38 levels) and safety
- To estimate the correlations between potential PD markers (FMX-MRI, TAM, tumor irinotecan, tumor SN-38 levels) and tumor response
- To characterize each tumor biopsy to permit multivariate comparative analyses between tumor characteristics, FMX-MRI signal and drug metabolite levels

Expansion Phase:

- To evaluate a set of potential biomarkers from tumor tissue and blood samples for their ability to predict PK and/or response to MM-398 treatment
Exploratory analyses will be performed ad-hoc only. When applicable, detailed analyses and results will be documented separately.

3 STUDY DESIGN

3.1 General Design and Plan

This study comprises two phases: pilot phase and expansion phase.

Pilot phase will enroll approximately 12 patients, up to 20 in total. The first three patients that are enrolled can have any solid tumor type; however subsequent patients must have NSCLC, CRC, TNBC, ER/PR positive breast cancer, pancreatic cancer, ovarian cancer, gastric cancer, gastro-oesophageal junction adenocarcinoma or head and neck cancer. No more than three patients with ER/PR positive breast cancer can be enrolled in the Pilot Phase and similar restrictions may be placed on other tumor types to ensure a heterogeneous population.

These indications were selected based on data suggesting that these tumor types have high levels of CD68 (tumor associated macrophages) and carboxylesterase enzyme (CES) activity or high levels of deposition, any of which may correlate to MM-398 response.

The Expansion Phase will enroll cohorts of single indications of patients with locally advanced or metastatic breast cancer in 3 cohorts of 10 patients each depending on sub-type of breast cancer:

- Cohort 1: ER and/or PR-positive breast cancer
- Cohort 2: Triple negative breast cancer (TNBC)
- Cohort 3: Breast Cancer (BC) with active brain metastasis

There are four stages to each phase of this study:

- Screening (-28d): patients undergo screening assessments to determine if they are eligible for the study
- Ferumoxytol (FMX) (Day 1 Day 2): patients receive ferumoxytol infusion and undergo required FMX-MRI scans and pre-treatment biopsy (if applicable, see Cohort requirements) prior to receiving MM-398
- MM-398 Treatment (C1D1 progression of disease): patients receive an MM-398 dose of 60 mg/m² every 2 weeks, which should be dose escalated to 80 mg/m² every 2 weeks in subsequent doses depending on patient tolerance, other required assessments, and undergo a post-treatment (MM-398) multiple pass core biopsy
- Follow up (+30d from last dose): patients return to clinic 30 days after their last dose of MM-398 for final safety assessments

Ferumoxytol magnetic resonance imaging (FMX-MRI) will be done for both pilot phase and expansion phase. The schedule for pilot phase FMX-MRI is: pre-dose of ferumoxytol, 1-4 hours post dose and 24 hours post dose of ferumoxytol.

The schedule for expansion phase is outlined in Tables 1 and 2:

Table 1 Summary of Expansion Phase MRI Scan Groups (Cohorts 1 and 2)

Scan group	N ^a	Baseline	Baseline (repeat)	1-4 h	24 h	24 h (repeat)	2 wk Baseline
1	5	X	X		X		X
2	5	X		X	X	X	
3	10	X		X	X		

- a. Enrollment into Scan Groups 1 and 2 may be increased at the discretion of the Sponsor, in the event that any of the images are not evaluable, or it is determined that more information is needed from the additional scan time points. In this case, enrollment into Scan Group 3 will be decreased by a corresponding number of patients.

For patients with active brain metastases enrolled into Cohort 3, the following FMX-MRI schedule will be followed:

Table 2 Expansion Phase Cohort 3 MRI Scan Time Points

Scan group	N	Baseline	Baseline (repeat)	1-4 h	24 h	24 h (repeat)	2 wk Baseline
Cohort 3	10	X ^a		X ^b	X ^a		

- a. Patients with extra-cranial disease will have MRIs of two body areas at baseline and 24 h: one brain scan and one body scan (body scan will capture the majority of the patient's extra-cranial disease; see imaging manual for details)
b. Brain scan only will be completed at this time point

A single dose of ferumoxytol will be administered at Day 1 by intravenous injection at a rate of up to 1 ml/sec (30 mg/second), with monitoring of vital signs. MM-398 will be administered by intravenous (IV) infusion over 90 minutes starting at a dose of 60 mg/m² every two weeks. The MM-398 period (C1D1) should begin within 7 days of the ferumoxytol infusion. The dose of MM-398 should be escalated to 80 mg/m² every two weeks depending on patient tolerance. Patients will be treated until disease progression or unacceptable toxicity.

Patients receiving ferumoxytol who do not complete all assessments and/or do not have evaluable FMX MR images may still proceed to the MM-398 treatment phase; however additional patients may be enrolled to ensure that adequate MRI data are collected to achieve the objectives of the study. In addition, in order to be considered pharmacodynamic evaluable for the Expansion Phase, patients must have received MM-398 and completed at least one CT scan at the 8-week post-treatment timepoint.

3.2 Treatment Assignment

All patients will be administered a single dose 5 mg/kg of ferumoxytol at Day 1 by intravenous infusion as an imaging agent. MM-398 will be administered at a dose of 60 mg/m² every two weeks starting at Cycle 1 Day 1 during MM-398 treatment phase.

3.3 Treatment Blinding

This is an open-labeled single treatment arm study. There is no treatment blinding.

4 SAMPLE SIZE DETERMINATION

No formal hypothesis testing is performed for this study. Therefore, the Pilot and Expansion Phases are not powered to detect statistical differences on any parameters. Results will be descriptive.

The Pilot Phase will enroll 12 to 20 patients with various indications, while the Expansion Phase will enroll approximately 30 metastatic breast cancer patients across three cohorts.

The Expansion Phase ORR is estimated to be around 29% with a 95% confidence interval (14.6-46.3) [Awada, 2013]. Other studies showed similar response rates ranging from 5-32% [Kümler, 2013]. Hypothesizing a true ORR of 30%, the probability of at least 14 responses of 30 evaluable patients would be 0.04. The probability of at least 13 responses would be 0.084.

5 SEQUENCE OF PLANNED ANALYSES

5.1 Interim Analyses

No interim analysis will be performed. Data may be analyzed while study is ongoing for administrative purposes.

5.2 Final Analyses

No formal hypothesis testing will be performed in the Pilot or Expansion Phases of this study. Descriptive statistics will be calculated to summarize categorical and continuous parameters. Parameters will be reported by study phase (pilot and expansion phase) and expansion phase will be further summarized by each cohort and total. When appropriate, the Pilot and Expansion study phases may be pooled. The final analysis will be conducted when the last patient enrolled in expansion phase discontinued study treatment for any reason or after the patient has been treated for six months, whichever comes first. A single cut-off date will be applied wherein all data for all patients up to that date will be included in the analysis and all data reported after the cut-off date will be excluded from analysis.

Exploratory analyses and/or post-hoc analyses completed to support planned study analyses, which were not identified in this SAP, will be documented and reported in appendices and/or addendum to the CSR.

Subsequent analyses of the data may be generated as needed per regulatory obligation.

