10.11 Sample Size and Statistical Hypothesis

No formal hypothesis testing will be performed for this study, therefore the Pilot and Expansion Phases are not appropriately powered to detect statistical differences. The Pilot Phase will enroll between 12 and 20 patients with various indications, while the Expansion Phase will enroll approximately 30 metastatic breast cancer patients across 3 cohorts.

For the Pilot Phase, Table 16 provides some probabilities of observing a particular adverse event.

True Event Rate	Probability to Observe	Probability to Observe
	at Least 1 Event	More than 1 Event
0.05	0.46	0.12
0.10	0.72	0.34
0.15	0.86	0.56
0.20	0.93	0.73
0.25	0.97	0.84

 Table 16: Probability to Detect an Adverse Event with N=12 Patients

The Expansion Phase ORR is estimated to be around 29% with a 95% confidence interval (14.6-46.3) [36]. Other studies showed similar response rates ranges ranging from 5-32% [33].

Hypothesizing a true ORR of 30%, the probability of at least 14 responses of 30 evaluable patients would be 0.04. The probability of at least 13 responses would be 0.084.

11 Extension Phase

Following fulfillment of analysis requirements, the Sponsor may elect to reduce follow-up to minimally required safety collection. Patients will be followed per standard of care to assess for safety and the required visits in the schedule of assessments are no longer applicable. All AEs meeting SAE reporting requirements or AESI for which the investigator feels are of greater incidence or severity than presented in the IB must be submitted as per section 9.3.

12 Study Administration

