6 ANALYSIS POPULATIONS

- **Screened population:** This population includes all patients screened (i.e. who signed the informed consent).
- **Safety population:** This population includes all patients receiving at least one dose of MM-398 or ferumoxytol. If ferumoxytol safety population is different from MM-398 safety population, safety analysis will be performed separately on both populations.

Depending upon patients receiving MM-398 and not ferumoxytol and vice versa, the safety population may be expanded in order to not dilute any adverse event rate:

- Ferumoxytol safety population: any patient receiving ferumoxytol. All analyses using this population will be based on the treatment actually received.
- MM-398 safety population: all patient receiving at least one dose of MM-398. All analysis using this population will be based on the treatment actually received.
- **Efficacy evaluable population**: This population includes all patients receiving at least one dose of MM-398. All statistical analyses of data on non-imaging related efficacy analyses will be performed using efficacy evaluable population.
- **Pharmacodynamic (PD) evaluable population**: This population includes all efficacy evaluable patients with the following: a) pre-treatment FMX-MRI scan(s) and b) radiological scans at 8 weeks. All statistical analyses of data on imaging related efficacy analyses will be performed using PD evaluable population.
- **Pharmacokinetic (PK) population**: This population includes patients receiving at least one dose of MM-398, and blood samples at the predefined timepoints adequately collected (with no major protocol deviations affecting the PK variables & with sufficient number of plasma concentrations to estimate the main PK parameters (C_{max}, AUC)). PK analysis will be documented in a separate SAP.

The term ‘All Screened Patients’ will be used to describe the set of all patients who signed informed consent, including patients who failed screening and any others who initiated screening.

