7.6.3 Study Periods

For the evaluation of safety, assessments will be assigned to study periods. These will be:

- Ferumoxytol safety period: from time of the first dose of ferumoxytol to the time of the first dose of MM-398. If an observation contains a date only, then the corresponding ferumoxytol safety period is the time from the date of the first dose of ferumoxytol to the day before the date of the first administration of MM-398. If the patient does not receive MM-398, the ferumoxytol safety period ends at 30 days after the date of the ferumoxytol dose.
- MM-398 safety period: from time of the first dose of MM-398 to 30 days after the date of the last study drug administration of MM-398. If an observation contains a date only, then the corresponding MM-398 safety period begins on the date of the first administration of MM-398.
- Events/observations will be assigned to study periods based on the start date or date and time if time is available.

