11.3.2.4 Clinical Benefit Response (CBR)

CBR₂₄ is defined as the proportion of patients with a BOR characterized as a Complete Response (CR) at any time, Partial Response (PR) at any time, or Stable Disease (SD) \geq 24 weeks relative to the total number of evaluable patients, expressed as a percentage. Evaluable patients are the treated patients with measurable disease at baseline.

The primary analysis for CBR will be based on the investigator-assessed response. CBR will be summarized by each cohort and overall for expansion phase and exact 95% confidence intervals based on the binomial distribution will be reported. The analyses will be performed for efficacy evaluable population.

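### SAP 5.2 ties one data cut-off for all patients to the last-enrolled patient; if that patient stops before week 24, ongoing stable disease in recent enrollees is scored as failure and CBR24 is biased downward

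*SAP*

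**What the plan says.** SAP 5.2 (Final Analyses) sets two alternative triggers, both read from one patient. The analysis falls due "when the last patient enrolled in expansion phase discontinued study treatment for any reason or after the patient has been treated for six months, whichever" is earlier. A single cut-off date then applies to all patients, and "all data reported after the cut-off date will be excluded from analysis". No minimum follow-up is required of anyone else, and the protocol offers no competing rule.

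SAP 11.3.2.4 defines CBR24 as CR or PR at any time, or SD lasting at least 24 weeks, "relative to the total number of evaluable patients, expressed as a percentage. Evaluable patients are the treated patients with measurable disease at baseline". It sets no minimum follow-up and has no rule for SD still ongoing at the cut-off.

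Other provisions that depend on the cut-off:
- SAP 6: the PD evaluable population, used for the imaging-related analyses, needs "a) pre-treatment FMX-MRI scan(s) and b) radiological scans at 8 weeks".
- SAP 11.3.2.3: for ORR, patients with too little data for classification count as non-responders.
- SAP 11.3.2.1 and 11.3.2.5: PFS and DOR have explicit censoring rules.
- SAP 7.6.3: the MM-398 safety period runs "from time of the first dose of MM-398 to 30 days after the date of the last study drug administration of MM-398".
- Protocol 5.4: Expansion patients who leave before the 8-week disease evaluation may be replaced, at the sponsor's discretion.

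**The concern.** The six-month limb alone would be adequate: six months is 26.1 weeks, so every patient would have at least 24 weeks of potential follow-up. The discontinuation limb removes that assurance. The last patient may stop at any time, and the data for all patients are then cut on one patient's outcome.

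The consequence for CBR24 is bias and not only lost precision. A patient with SD who is still on treatment at, say, week 15 has not failed, but is counted in the denominator and cannot enter the numerator. CBR is one of the two efficacy indicators named in the Expansion Phase secondary objectives, and the size of the bias depends on how one patient fares.

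**Working it through.** **Plan's own figures.** The cut-off rule carries no derived figure. The only calculation stated nearby (SAP 4) reproduces: with n = 30 and true ORR 0.30, P(at least 14 responses) = 0.0401 and P(at least 13) = 0.0845, against 0.04 and 0.084 stated. It does not bear on this point.

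**Inputs from the documents.** About 30 Expansion patients in three cohorts of 10; disease evaluation every 8 weeks, within 7 days either side; CBR24 as defined in SAP 11.3.2.4; six months = 365.25/2/7 = 26.1 weeks.

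**Assumptions, not in the documents.** Accrual of 1, 2 or 3 patients per month; exponential time on treatment with median m of 8, 12 or 16 weeks, standing in for duration of disease control.

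**Step 1: who is cut short, with even accrual.** If the last patient stops at week t, the k-th patient enrolled before has t + k × gap weeks of potential follow-up. The gap is 4.35, 2.17 or 1.45 weeks at 1, 2 or 3 per month. For example, at 2 per month and t = 8, 8 + 7 × 2.17 = 23.2 is under 24 and 8 + 8 × 2.17 = 25.4 is not, so 7 patients fall short.

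| Last patient stops at week | Others under 24 weeks (1 / 2 / 3 per month) | Others under 8 weeks |
|---|---|---|
| 2 | 5 / 10 / 15 | 1 / 2 / 4 |
| 8 | 3 / 7 / 11 | 0 / 0 / 0 |
| 16 | 1 / 3 / 5 | 0 / 0 / 0 |

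**Step 2: how often.** P(last patient stops before week 24) = 1 − 2^(−24/m), which is 0.875, 0.75 and 0.646 for m = 8, 12 and 16.

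**Step 3: expected loss in CBR24.** Let λ be accrual per week (12/52.18 = 0.230 at 1 per month), θ = m/ln 2, S = 2^(−24/m) the share lasting 24 weeks, and A(w) = w − θ(1 − 2^(−w/m)) the expected shortfall of the last patient's treatment time below w weeks.

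- (a) No long-duration patient responds: loss = λ × S × A(24) / 30.
- (b) Half of them respond, first seen at week 8 or 16 with equal chance: loss = λ × S × [0.5 A(24) + 0.25 A(16) + 0.25 A(8)] / 30.
- (c) As (b), and the last patient reaches week 8: loss = λ × S × [0.5 A(16) + 0.25 A(8)] / 30.

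| Accrual, median | S | A(24) | A(16) | A(8) | (a) | (b) | (c) |
|---|---|---|---|---|---|---|---|
| 1/month, 8 wk | 0.125 | 13.90 | 7.34 | 2.23 | 1.3 | 0.9 | 0.4 |
| 2/month, 12 wk | 0.250 | 11.02 | 5.56 | 1.59 | 4.2 | 2.8 | 1.2 |
| 3/month, 16 wk | 0.354 | 9.08 | 4.46 | 1.24 | 7.4 | 4.8 | 2.1 |

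Losses are in percentage points. For the middle row, (a) is 0.460 × 0.25 × 11.02 / 30 = 4.2 points, that is 25.0% observed as 20.8%. The first and last rows are the extremes of the nine combinations. A simulation of 40,000 trials per setting with random accrual agrees.

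**Step 4: weight of one patient.** 1/30 = 3.3 points overall; 1/10 = 10 points in a cohort.

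**The case against.** Several points on the other side have force.

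- **Replacement.** A last patient who leaves before the 8-week evaluation may be replaced under Protocol 5.4, and the replacement becomes the last enrolled. That covers most very early stops. It is discretionary, and it does not reach stops between weeks 8 and 24.
- **Responders are protected.** CR or PR at any time counts. Case (a) ignores this, and its middle row gives a CBR of 25.0%, below the 29–30% ORR that the SAP itself assumes. It is therefore an upper bound.
- **Imprecision is larger.** The exact 95% interval for 8/30 is 12% to 46%. The study is descriptive, so no error rate is affected.
- **Cut-off date and trigger date.** SAP 5.2 does not expressly equate them. Equating them is the natural reading; if another date is meant, it is undefined.

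A reader might also infer more than the text supports:
- **The FMX-response analysis will lose patients.** Missing 8-week scans, and the matching non-responder scoring in ORR, arise only if the last patient stops before about week 8 and is not replaced. Otherwise best change in tumour size is simply taken over fewer scans.
- **PFS and DOR are biased.** They lose follow-up, but through censoring.
- **The missing scans can never be recovered.** Protocol 11 (Extension Phase) says only "Following fulfillment of analysis requirements, the Sponsor may elect to reduce follow-up to minimally required safety collection". That is an option, not an automatic lapse, and SAP 5.2 allows post-hoc analyses.

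**Conclusion.** The point stands for CBR24. As written, the rule can score ongoing SD as failure because one other patient stopped treatment, and nothing in the SAP corrects for it. The expected loss is at most 1.3 to 7.4 points across the assumed settings, about 0.9 to 5 points if half of the long-duration patients respond by week 8 or 16, and about 0.4 to 2 points if the last patient also reaches week 8. These figures rest on assumed accrual, treatment duration and response timing. The direction of the bias does not.

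The average is modest, but the effect falls in whole patients, which matters in cohorts of 10. The last patient's 30-day safety window may also fall after the cut-off; that concerns one patient's final events and depends on the cut-off being the trigger date. This is worth correcting, but it does not undermine the primary FMX objective.

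**What to change.** In SAP 5.2, define the cut-off explicitly as the date by which every Expansion patient has either (a) discontinued MM-398 and completed the 30-day follow-up visit, or (b) completed the 24-week disease evaluation or six months of treatment.

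If an earlier cut-off must be kept, report CBR24 only in patients first dosed at least 25 weeks before it (24 weeks plus the 7-day scan window), whatever their outcome, and state how many are excluded. Selecting on first-dose date alone avoids selecting on response.

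The cost is SAP wording and a possible delay of up to about six months after the last enrolment, plus the 30 days to the follow-up visit if a patient stops late in that period. The six-month limb of the current rule already accepts essentially the same wait.

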6 ANALYSIS POPULATIONS

- **Screened population:** This population includes all patients screened (i.e. who signed the informed consent).
- **Safety population:** This population includes all patients receiving at least one dose of MM-398 or ferumoxytol. If ferumoxytol safety population is different from MM-398 safety population, safety analysis will be performed separately on both populations.

Depending upon patients receiving MM-398 and not ferumoxytol and vice versa, the safety population may be expanded in order to not dilute any adverse event rate:

- Ferumoxytol safety population: any patient receiving ferumoxytol. All analyses using this population will be based on the treatment actually received.
- MM-398 safety population: all patient receiving at least one dose of MM-398. All analysis using this population will be based on the treatment actually received.
- **Efficacy evaluable population**: This population includes all patients receiving at least one dose of MM-398. All statistical analyses of data on non-imaging related efficacy analyses will be performed using efficacy evaluable population.
- **Pharmacodynamic (PD) evaluable population**: This population includes all efficacy evaluable patients with the following: a) pre-treatment FMX-MRI scan(s) and b) radiological scans at 8 weeks. All statistical analyses of data on imaging related efficacy analyses will be performed using PD evaluable population.
- **Pharmacokinetic (PK) population**: This population includes patients receiving at least one dose of MM-398, and blood samples at the predefined timepoints adequately collected (with no major protocol deviations affecting the PK variables & with sufficient number of plasma concentrations to estimate the main PK parameters (C_{max}, AUC)). PK analysis will be documented in a separate SAP.

The term ‘All Screened Patients’ will be used to describe the set of all patients who signed informed consent, including patients who failed screening and any others who initiated screening.

